12.1	FUNDING SOURCE	19
12.2	CONFLICT OF INTEREST	19
12.3	DISCLOSURE	20
12.4	SUBJECT STIPENDS OR PAYMENTS.....	20
13	PUBLICATION PLAN	20
14	REFERENCES.....	20
15	ATTACHMENTS	21

CONFIDENTIAL

This material is the property of the Loma Linda University Medical Center. Do not disclose or use except as authorized in writing by the study sponsor

List of Abbreviations

CRF	Case Report Form
FDA	Food and Device Administration
GCP	Good Clinical Practice
IRB	Institutional Review Board
HA	Hydroxyapatite
PLA	Poly-lactic acid
PEG	Polyethylene glycol
CABG	Coronary Artery Bypass Grafting
OR	Operating Room

CONFIDENTIAL

This material is the property of the Loma Linda University Medical Center. Do not disclose or use except as authorized in writing by the study sponsor

Study Summary

Title	Effectiveness of BoneSeal® on sternal bone hemostats in patients undergoing cardiothoracic surgery
Short Title	Effectiveness of BoneSeal®
Protocol Number	Not yet assigned
Methodology	Prospective, randomized, open-label, study design
Study Duration	Estimated duration for the main protocol (start of screening November 2016) to (last subject processed and finishing the study November 2017)
Study Center(s)	Single-center
Objectives	To evaluate the effectiveness of BoneSeal® on bone hemostats in patients undergoing cardiothoracic surgery.
Number of Subjects	60
Diagnosis and Main Inclusion Criteria	Adult patients over 18 years undergoing coronary artery bypass grafting with or without valve replacement or repair ultimately requiring a sternotomy.
Study Product, Dose, Route, Regimen	BoneSeal® Bone Wax Hemostats Dosage regimen is as follows: 1 to 2 units (2.5 or 3.5 grams) per surgery as determined by the surgeon.
Reference therapy	Ostene®
Statistical Methodology	Statistical methods for evaluating postoperative bleeding and need for blood transfusions will include a Fisher's exact test (2 groups, 2 outcomes).

CONFIDENTIAL

This material is the property of the Loma Linda University Medical Center. Do not disclose or use except as authorized in writing by the study sponsor

1 Introduction

This document is a protocol for a human research study. This study is to be conducted according to US and international standards of Good Clinical Practice (FDA Title 21 part 312 and International Conference on Harmonization guidelines), applicable government regulations and Institutional research policies and procedures.

1.1 ***Background***

During cardiothoracic surgery a sternotomy is used to access the mediastinum. The procedure can often result in significant bleeding from the sternal bone marrow. It has been estimated that sternal bone marrow is responsible for more than 80% of bloodshed in cardiac surgery requiring sternotomy. This leads to increased chance of blood and blood products usage. Blood products transfusions has been shown extensively in the literature to increase both mortality and morbidity. The shortage and exponentially increasing costs adds to this major problem. In order to reduce the possibility of complications resulting from the bleeding, surgeons often use several hemostatic agents on the cut sternal site. Surgical beeswax, an often used substance, is a mixture of sterilized honeybees wax and paraffin wax (1). The resulting hydrophobic bone wax is pliable and easily used to form a physical barrier on the cut spongy bone, occluding the bleeding channels (2). However, the material is not readily absorbed which prevents bone regrowth and possibly leads to infection (3) (4) (5) (6). Other alternative substances have been reported, though the lack wide spread adaptation of these products may be due to the expense of the material and/or the handling properties of the product (7) (8) (9) (10) (11). Ostene®, an alkaline oxide copolymer bone hemostatic material, has been show to achieve immediate hemostasis as compared to bone wax, however, unlike bone wax, the material is water soluble substance had complete dissolved in 3 weeks and bone regrowth was observed (12). While Ostene® is water soluble and thus does not inhibit bone regrowth, it does not appear to promote bone growth (12). Ostene®, can also dissolve within a few minutes and sternal bleeding can continue throughout the case.

1.2 ***Investigational Agent***

BoneSeal® (an FDA cleared product) is an absorbable synthetic, with beeswax consistency, bone hemostatic agent that also contains PLA, PEG and hydroxyapatite which supports bone re-growth. The product is packaged as 5 single use, sterile units (2.5 or 3.5 gram ingot) per carton. One sterile unit contains one ingot. Sterilization is by gamma irradiation. BoneSeal® has FDA 510k clearance (K142348).

CONFIDENTIAL

This material is the property of the Loma Linda University Medical Center. Do not disclose or use except as authorized in writing by the study sponsor

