1.5 Dose Rationale and Risk/Benefits

Dosage regimen is as follows: 1 to 2 units (2.5 or 3.5 grams) per surgery as determined by the surgeon. This is based on the common amount of the comparable product used and the amount needed to obtain immediate hemostasis during surgery.

2 Study Objectives

A prospective randomized open-label study that will evaluate the effectiveness of the pliable and absorbable bone hemostats (BoneSeal®) composed of synthetic materials and hydroxyapatite on the reduction of bleeding from the sternal bone marrow in patients undergoing Coronary Artery Bypass Grafting, with or without valve replacement or repair. This product will be compared to the similar, currently used product, Ostene®. Bleeding will be evaluated qualitatively by the surgeon as well as quantitatively by comparing pre- and post-operative hemoglobin levels, intra-operative and post-operative blood product usage, and post-operative chest tube output. A 30 day follow-up will be conducted to evaluate the patient's tolerance of the product, possible complications, or infection. Additionally, surgeons will be asked to comment on the ease of use of the product.

3 Study Design

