3.2 Primary Study Endpoints

- 1) Qualitative determination of bleeding and hemostatic action during application graded by the surgeon using the mild, moderate, and severe for bleeding and complete, moderate, minimal, and failure for hemostatic action.

CONFIDENTIAL

This material is the property of the Loma Linda University Medical Center. Do not disclose or use except as authorized in writing by the study sponsor

- 2) Occurrence of re-bleeding during the operation will be noted. Reapplication of product will not occur.
- 3) Postoperative hemoglobin as compared to baseline preoperative readings.
- 4) Post-operative chest tube output.
- 5) Intra-operative and post-operative blood product transfusion quantities.
- 6) Sternal wound infection or other complications within 30 days post procedure.

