5.5.4 Return or Destruction of Study Device

At the completion of the study, there will be a final reconciliation of device shipped, device consumed, and device remaining. This reconciliation will be logged on the device reconciliation form, signed and dated. Any discrepancies noted will be investigated, resolved, and documented prior to return or destruction of unused study device. Device destroyed on site will be documented in the study files.

6 Study Procedures

6.1 Study Data Point 1

Hemostasis during surgery will be determined by surgeon's qualitative evaluation. Notation of re-bleed will be made. Re-application of product will not occur.

6.2 Study Data Point 2

Postoperative bleeding will be evaluated by documentation surgical site drainage and the use of blood products.

6.3 Study Data Point 3

30 day post-op follow-up to all for sufficient time to heal and evaluate for possible post-operative infection or complications. This evaluation can be conducted either in person or by phone.

CONFIDENTIAL

This material is the property of the Loma Linda University Medical Center. Do not disclose or use except as authorized in writing by the study sponsor

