6.4 Schedule of Events

Pre-Operative	Study Data Point 1 – Intra-Operative Hemostasis Evaluation	Study Data Points 2 – Post-Operative 24 hours	Study Data Point 3 – Post-Operative 30 Day Follow-up by phone
Inclusion/Exclusion	Notation of severity of osteoporosis	Hemoglobin Levels	Survival Documentation
Informed Consent	Qualitative evaluation osteoporosis during surgery	Notation of post- operative blood product usage	Notation of any visits for infection or complications.
Hemoglobin levels	Qualitative evaluation of bleeding of the cut sternum during the surgery	6 hours Post-op Surgical Site Drainage	
	Qualitative evaluating of the ease of use of the product	12 hours Post-op Surgical Site Drainage	
	Notation of in- operative blood product usage	18 hours Post-op Surgical Site Drainage	
	Notation of a re-bleed occurrence	24 hours Post-op Surgical Site Drainage	

7 Statistical Plan

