7.1 Sample Size Determination

The power of 60 patients was not determined statistically. The number was determined at the request of the sponsor based on their minimum requirements. In order to compensate for the lack of statistical sample size determination, an increase in alpha and adding an ANCOVA to explain any differences found will be utilized.

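### Three quantitative primary endpoints (hemoglobin, chest tube output, transfusion quantities) have no usable between-arm analysis on their own scale

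*Combined protocol and SAP*

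**What the plan says.** All references are to the combined protocol and SAP.

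- **Objective (section 2):** "Bleeding will be evaluated qualitatively by the surgeon as well as quantitatively by comparing pre- and post-operative hemoglobin levels". The sentence goes on to blood product usage and chest tube output.
- **Primary endpoints (3.2):** item 3 is "Postoperative hemoglobin as compared to baseline preoperative readings", item 4 is "Post-operative chest tube output" and item 5 is "Intra-operative and post-operative blood product transfusion quantities". All three are quantities.
- **Measurement (6.2 and 6.4):** "Postoperative bleeding will be evaluated by documentation surgical site drainage and the use of blood products". The schedule records drainage at 6, 12 and 18 hours and ends with "24 hours Post-op Surgical Site Drainage". It also lists hemoglobin before surgery and in the 24-hour post-operative column.
- **Study Summary, Statistical Methodology:** "Statistical methods for evaluating postoperative bleeding and need for blood transfusions will include a Fisher's exact test (2 groups, 2 outcomes"). No category or cut-off is given.
- **Section 7.1:** the 60 patients were not sized statistically; in compensation, "an increase in alpha and adding an ANCOVA to explain any differences found will be utilized". No alpha value, outcome or covariate follows.
- **Section 7.2:** one sentence of descriptive statistics. It covers drainage and omits hemoglobin and transfusion.
- **Section 7.3:** defines the all-randomized population only.

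**The concern.** The objective and endpoints promise quantitative comparisons, while the one named test needs two categories. Two analysts following this plan could report different tests for the same primary endpoint. One could cut drainage at a value of their choosing and run Fisher's test, and another could report means only. A third could fit an ANCOVA to whichever outcome they took section 7.1 to mean.

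The trial is open-label, so a cut-off or ANCOVA outcome settled after data are seen could be settled with the result in view. If drainage is cut into two, information already collected is discarded in a small sample that has no power calculation behind it.

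**Working it through.** **Step 1: endpoints against methods.**

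| Primary endpoint (3.2) | Study Summary | 7.1 | 7.2 |
|---|---|---|---|
| Hemoglobin vs baseline | not mentioned | ANCOVA, outcome not named | not mentioned |
| Chest tube output | covered only if postoperative bleeding is read through 6.2; 2x2 Fisher, no cut-off | same | descriptive only |
| Transfusion quantities | need for transfusion (yes/no) by Fisher; quantity not mentioned | same | not mentioned |

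Drainage has two open readings. Either it is cut into two categories at an unstated value, or it is only described and has no between-arm test.

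**Step 2: size of the loss under the first reading only.** The plan gives no alpha, power, effect size, SD or allocation ratio, so it has no figure of its own to reproduce. Assumed: 60 patients split 30/30, normal outcome with equal SDs on the analysis scale, two-sided alpha 0.05.

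- *t-test.* With 58 degrees of freedom the critical value is 2.002. The noncentrality is d × √(30/2) = d × √15. Solving for 80% power gives d = 0.7356 SD, that is, noncentrality 0.7356 × 3.873 = 2.849.
- *Cutting the outcome.* With the control mean at 0, the other mean at −d and a cut at c, the proportions above the cut are 1 − Φ(c) and 1 − Φ(c + d).
- *Fisher power.* Sum the product of the two binomial probabilities over all 31 × 31 tables with Fisher p ≤ 0.05.
- *Separating the causes.* Fisher's true size is below nominal (0.027 when both rates are 50%). Two comparators of about 5% size on the same tables are used: a randomized Fisher test (exactly 5%) and the pooled z-test. Comparator minus Fisher is conservatism; 80% minus comparator is the cut.

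| Cut | Rates | Fisher | Randomized Fisher / pooled z | Conservatism (points) | Cut (points) |
|---|---|---|---|---|---|
| Midway between arm means | 0.643 vs 0.357 | 52% | 60% / 62% | 8 to 10 | 18 to 20 |
| Control median | 0.500 vs 0.231 | 48% | 58% / 58% | 10 | 22 |
| Control upper quartile | 0.250 vs 0.079 | 29% | 42% / 44% | 13 to 15 | 36 to 38 |

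**Step 3: raised alpha.** Section 7.1 says alpha will be increased but gives no value. At 0.10, the same 0.7356 SD shift gives the t-test 88% and Fisher 62%, 60% and 41% for the three cuts. The loss remains.

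**Step 4: multiplicity once the methods are named.** Hemoglobin, drainage, transfused quantity, any transfusion and re-bleeding make five tests. If they are treated as independent (an assumption), the chance of at least one false positive is 1 − 0.95⁵ = 23% at alpha 0.05 and 1 − 0.90⁵ = 41% at 0.10.

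**The case against.** The strongest reply is that the plan does assign a method. The Study Summary ties Fisher's test to postoperative bleeding, and 6.2 says how that bleeding is evaluated. The Summary's wording is also not exclusive, 7.2 covers drainage, and the ANCOVA shows that a quantitative analysis was in mind.

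Part of this stands. A reader might infer that the plan names no test at all for drainage or transfusion. The documents do not support that: a test is nominally assigned, and for any transfusion it is appropriate and needs no cut-off. Only hemoglobin is absent from every statistical statement.

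The rest does not close the gap. Non-exclusive wording names no other method. A descriptive summary is not a comparison with the control product. The ANCOVA has no outcome or covariate, and it is framed as explaining differences that some other analysis has already found.

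It is also fair to say that the power figures rest on assumptions and that the tests proposed below are one defensible set among several. Both are accepted. The finding is textual; the figures only show that the open choice matters.

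**Conclusion.** The point holds. None of the three quantitative primary endpoints has a usable between-arm analysis on its own scale. For drainage and transfused quantity the method is undefined or unsuited; for hemoglobin none is stated.

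If Fisher's test is applied to drainage, power falls from 80% to between 29% and 52%, under the assumed 30 per arm, normality, 0.7356 SD shift and alpha 0.05. It would be wrong to attribute all of that to the cut: about 8 to 15 points are Fisher's conservatism and about 18 to 38 are the cut. If drainage is only described, there is no Fisher loss, and the defect is a primary endpoint without a comparison. The figures do not carry over to hemoglobin or transfused quantity.

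A reader might also infer that cut-offs or outcomes will be chosen to suit the result. The documents show only that nothing prevents it. The data remain analysable, so this is a change that should be made rather than one on which the trial fails.

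**What to change.** Amend the Study Summary, 7.1 and 7.2 as follows.

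1. **Hemoglobin.** Make the ANCOVA of 7.1 a prespecified comparison of 24-hour post-operative hemoglobin between arms, adjusted for pre-operative hemoglobin, with a confidence interval. Run it whether or not a difference has been found. Report it beside transfusion by arm, because transfusion raises hemoglobin and the model does not correct for that.
2. **Chest tube output.** State whether this is the surgical site drainage of 6.4, and whether the 6, 12, 18 and 24-hour readings are interval or running totals. Compare the 0 to 24-hour total on its quantitative scale. One option is a t-test on logs, with any constant for zeros fixed in advance, reported as a ratio of geometric means with a confidence interval.
3. **Transfusion quantity.** Define the products and units, sum intra- and post-operative amounts, and compare arms by the Wilcoxon rank-sum test with a location-shift estimate and interval.
4. **Binary outcomes.** Keep Fisher's exact test for any transfusion and for re-bleeding.
5. **Error rate.** Give the numeric alpha. State that these are several primary comparisons and either set a multiplicity rule or acknowledge the inflation shown above.

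Equivalent prespecified quantitative tests would serve as well.

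**Cost:** wording, slightly more analysis work and back-transformation of the drainage result. No patients, visits or measurements are added. The change does not decide which of the six primary endpoints leads.

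### Need for transfusion has only an unadjusted Fisher's exact test, although pre-operative hemoglobin is collected; pre-specify a hemoglobin-adjusted analysis and keep Fisher as the sensitivity analysis

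*Combined protocol and SAP*

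**What the plan says.** - **Study Summary, Statistical Methodology.** The approach to postoperative bleeding and "need for blood transfusions will include a Fisher's exact test", specified for two groups and two outcomes. No covariate is mentioned.
- **3.2, endpoint 5.** Transfusion is listed among the primary endpoints as a quantity: "Intra-operative and post-operative blood product transfusion quantities".
- **3.2, endpoint 3.** "Postoperative hemoglobin as compared to baseline preoperative readings" is another primary endpoint, so a baseline hemoglobin value is needed for each patient. The pre-operative column of the 6.4 schedule includes it.
- **5.3.** Allocation is by sealed envelope on the day of surgery. No ratio, blocking or stratification is described.
- **7.1.** "The power of 60 patients was not determined statistically". To compensate, "an increase in alpha and adding an ANCOVA to explain any differences found will be utilized". The value of alpha is not given, nor are the outcome and covariates of the ANCOVA.
- **7.2.** Only descriptive statistics are listed. Fisher's test is not repeated, and no model for transfusion appears.

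**The concern.** A 2x2 table cannot use a baseline value that is already in hand and that plausibly predicts transfusion. With about 30 patients per arm and no stratification described, the arms can differ in starting hemoglobin by chance. The crude risk difference then carries that imbalance with it. Fisher's test also spends only about half of its nominal error rate at this size, so a real difference is missed more often than necessary.

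The ANCOVA in 7.1 does not close the gap. It comes after a difference is found, it has no stated outcome or covariate, and a linear model does not naturally suit a yes/no outcome. Transfusion is one of the listed primary endpoints, and the sample size has no statistical basis, so it matters how efficiently the 60 patients are used.

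**Working it through.** **The plan's own figure.** The sample size of 60 comes with no event rate, effect, alpha or power, so there is nothing to reproduce.

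**Inputs.** From the documents: N = 60, a two-group two-outcome Fisher test, and an alpha that is raised to an unstated value. Assumed, because the documents are silent: 1:1 allocation (30 per arm), no dropout, two-sided alpha of 5% (10% as an alternative), the transfusion rates, hemoglobin SD 1.6 g/dL, and the hemoglobin-transfusion association.

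**Step 1: actual size of Fisher's test.** Full enumeration at 30 per arm with equal true rates of 30%, 50% or 70% gives 2.6 to 2.7% at nominal 5% and 5.2 to 5.6% at nominal 10%.

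**Step 2: power for 50% vs 25%, nominal 5%.** Fisher has 41.3% by enumeration. The others are simulated. LRT is the likelihood-ratio test from logistic regression.

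| Odds ratio per g/dL | Equivalent per SD | Fisher | Unadjusted LRT | Adjusted LRT |
|---|---|---|---|---|
| 0.7 | 1/0.7^1.6 = 1.8 | 41% | 52-54% | 56% |
| 0.5 | 1/0.5^1.6 = 3.0 | 41% | 52-54% | 62% |
| 0.4 | 1/0.4^1.6 = 4.3 | 41% | 52-54% | 66% |

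At an odds ratio of 0.5 the total gap is 62 - 41 = 21 points. About 53 - 41 = 12 come from replacing Fisher and about 62 - 53 = 9 from hemoglobin. Across simulation runs hemoglobin's share is about 2 to 3 points at 0.7, 9 to 10 at 0.5 and 13 to 14 at 0.4. With no association (odds ratio 1.0) the adjusted test still reaches 53%, against 43% for Fisher in the same run, and hemoglobin contributes nothing.

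**Step 3: other rates, nominal 5%** (20,000 simulated trials each; Fisher exact; odds ratios per SD).

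| Comparator vs device | Fisher | Unadjusted LRT | Adjusted LRT at 1.5 / 2 / 3 |
|---|---|---|---|
| 50 vs 30% | 26% | 36% | 37 / 40 / 44% |
| 50 vs 20% | 60% | 72% | 73 / 75 / 79% |
| 30 vs 10% | 37% | 53-54% | 52 / 55 / 59% |
| 70 vs 40% | 56% | 66% | 68 / 71 / 76% |

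Hemoglobin's share is about -1 to +2 points at 1.5, +1 to +4 at 2 and +5 to +9 at 3. Leaving Fisher accounts for about 10 to 17 points.

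**Step 4: size of the adjusted test.** 5.2 to 6.1% at nominal 5%. When it is calibrated to exactly 5%, its power in the Step 2 scenarios is 54%, 61% and 64%, so its mild liberality explains only about 1 to 3 points.

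**Step 5: chance imbalance.** The standard error of the difference in mean hemoglobin is sqrt(2/30) = 0.258 SD, or 1.6 x 0.258 = 0.41 g/dL. The chance of a difference above 0.25 SD (0.4 g/dL) is 33%; above 0.5 SD (0.8 g/dL) it is 5.3%. Given a difference above 0.5 SD, no true effect and a 50% event rate:

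| Odds ratio per SD | Mean spurious risk difference | Fisher rejects at 5% |
|---|---|---|
| 1.5 | 6 points | 4.4% |
| 2 | 9 points | 6.2% |
| 3 | 13 points | 9.9% |

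The adjusted test rejects in 5.7 to 6.2% of these trials.

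**The case against.** An unadjusted test is a legitimate primary choice in a randomised trial. A reader might infer that Fisher's test is invalid here, or that it mistakes imbalance for a product effect. The documents do not support that. Chance imbalance is already inside the test's overall error rate, which stays below nominal. Even among the roughly 5% of trials with a large imbalance, Fisher's rejection rate is clearly above nominal only under the strongest association in Step 5. This stands. The case for adjustment is precision and a better estimate, not repair of an invalid test.

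A reader might also credit hemoglobin with the whole 15 to 25 points between Fisher and the adjusted test (56 - 41 to 66 - 41). Step 2 shows that about 12 of those points need no covariate. The documents give no transfusion rate, hemoglobin SD or strength of association, and an odds ratio of 0.5 per g/dL is already strong.

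Third, 7.1 raises alpha. At 10%, Fisher's actual size is about 5% and its power for 50% vs 25% is 53%, the same as the unadjusted likelihood-ratio test at 5%. This stands too, but the plan states no value, and a higher alpha does not address imbalance.

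Last, it would be wrong to say that the plan ignores adjustment. The wording is that methods will include Fisher's test, and 7.1 does promise an ANCOVA. A linear model could be applied to transfusion quantities, but nothing in 7.1 says that it will be. Its trigger, differences already found, also makes it an explanation after the event and not a pre-specified comparison.

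**Conclusion.** The point holds as a worthwhile, inexpensive improvement to a stated method. The only test named for need for transfusion is unadjusted, and no pre-specified analysis of that outcome uses the baseline hemoglobin that the schedule collects.

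Under the Step 2 assumptions, moving from Fisher to the adjusted test raises power from about 41% to between 56% and 66%. Hemoglobin's own part is about 2 to 14 points there, and about none if the association is weak. Protection of the estimate against chance imbalance is the second benefit. The direction is the same in every scenario; the size rests on assumed rates, SD, association, allocation and alpha.

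It should not be read as a rescue of the sample size. At two-sided 5% no scenario examined reaches 80% (the highest is 79%). At 10% the adjusted test reaches about 78 to 87% for the assumed 30-point differences, but only about 50 to 71% for the 20-point ones. The unjustified sample size, the unstated alpha and the six co-listed primary endpoints are larger problems than this one.

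**What to change.** Before any outcome data are seen:

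1. **Study Summary and 7.2.** Make the main comparison of need for transfusion a logistic regression on arm and continuous pre-operative hemoglobin, tested by likelihood ratio, with Firth penalisation under a stated rule if events are sparse. Report the standardised (marginal) risk difference with a 95% CI and name the variance method.
2. **Sensitivity analysis.** Keep Fisher's exact test in that role and say that the adjusted result takes precedence.
3. **Endpoint definition.** Reconcile endpoint 5 in 3.2, which is a quantity, with the two-outcome wording in the Study Summary. Apply the same hemoglobin adjustment to units transfused, using a count or ordinal model.
4. **7.1.** State the value and sidedness of alpha. Name the outcomes and covariates of the ANCOVA, and remove the condition that a difference must be found first.

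The cost is a few sentences and no new data. The downside is reliance on a simple model and a slightly liberal test at 60 patients (size about 5 to 6% at nominal 5%). The retained Fisher test covers this.

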5.3 Method for Assigning Subjects to Treatment Groups

Subjects will be randomized on the day of surgery. A number will be assigned to each package – study device and control. This number will be printed on a page and a page sealed that is then sealed in an envelope. On the day of surgery, an envelope will be pulled and opened by the OR Coordinator and confirmed by the investigator. The corresponding number will be selected from the labeled packages. The printed number will be labeled with the subject's information filed as a source document. The number and corresponding assignment (study device or control) will be noted in the patient's record.

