7.3 Subject Population(s) for Analysis

- All-randomized population: Any subject randomized into the study, regardless of whether they received study device

8 Safety and Adverse Events

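### Fisher's exact test, the only test named for yes/no outcomes, is valid but conservative with 60 patients; Boschloo's exact test would add about 2.5 to 9 points of power at an assumed 30 per arm and two-sided 0.05

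*Combined protocol and SAP*

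**What the plan says.** The Study Summary is the only place where a test for a two-category outcome is named. It reads "Statistical methods for evaluating postoperative bleeding and need for blood transfusions will include" Fisher's "exact test (2 groups, 2 outcomes". Section 7.2 lists descriptive statistics and no test.

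Section 7.1 says of the sample size: "The power of 60 patients was not determined statistically". As compensation it offers "an increase in alpha and adding an ANCOVA to explain any differences found will be utilized". The ANCOVA named there is not a test for yes/no data, and the size of the alpha increase is not given.

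Section 3.2 adds a further yes/no primary endpoint ("Occurrence of re-bleeding during the operation will be noted") and attaches no test to it.

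**The concern.** Only two arms are compared on a yes/no outcome, and the total number of events is not known in advance. Fisher's test nevertheless conditions on that total. With about 30 patients per arm the conditional distribution is coarse, so the test cannot spend its full nominal alpha. Its true error rate falls below the nominal level and it loses power.

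This matters more than usual here because section 7.1 concedes that the sample size has no statistical basis and proposes a looser alpha to make up for it. The named test leaves part of the present allowance unused, and another exact test can recover some of it without loosening anything.

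The point covers only endpoints that are truly yes/no. It does not concern how hemoglobin, drainage or transfusion quantities are analysed.

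**Working it through.** **Inputs**

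- Test: Fisher's exact, 2×2 (Study Summary).
- Total: 60 (Study Summary; section 7.1). The analysis set in section 7.3 is "Any subject randomized into the study, regardless of whether they received study device", and no dropout rate is given, so up to 60 are analysed.
- Alpha and sidedness: no value stated. Two-sided 0.05 is assumed, with 0.10 as a sensitivity case because section 7.1 announces an increase.
- Split: section 5.3 says only that "an envelope will be pulled and opened by the OR Coordinator and confirmed by the investigator", with no ratio or blocking. 30/30 is assumed, and 29/30, 29/31 and 28/32 are also run.
- Event rates: none stated. All rates below are assumptions.

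The plan has no power figure of its own to reproduce.

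**Step 1: Fisher's p-value.** With arm sizes n1 and n2 and t events in total, P(X1 = k | t) = C(n1,k)·C(n2,t−k)/C(n1+n2,t). The two-sided p_F sums these probabilities over all k that are no more likely than the observed one.

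**Step 2: true error rate.** Size = max over p of Σ b(x1; n1, p)·b(x2; n2, p), where b is the binomial probability and the sum runs over all tables that the test rejects.

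**Step 3: Boschloo's p-value.** p_B(table) = max over p of the probability of all tables whose p_F is no larger than the observed p_F. For every t, P(p_F ≤ c | t) ≤ c. Averaging over t keeps that bound for every p, so p_B ≤ p_F. The test therefore rejects everything Fisher rejects, and its size is at most alpha by construction. Enumeration at 30/30, 29/31 and 28/32, at 0.05 and 0.10, confirmed both properties.

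| Split, nominal alpha | Fisher size | Boschloo size |
|---|---|---|
| 30/30, 0.05 | 2.7% | 4.7% |
| 29/30, 0.05 | 3.6% | 4.7% |
| 29/31, 0.05 | 3.9% | 4.7% |
| 28/32, 0.05 | 3.7% | 5.0% |
| 30/30, 0.10 | 5.6% | 9.9% |

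**Step 4: power.** This is the sum in Step 2 with a different rate in each arm. At 30/30 and 0.05:

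| Assumed rates | Fisher | Boschloo | Gain (points) |
|---|---|---|---|
| 50% vs 20% | 59.6% | 67.1% | 7.5 |
| 60% vs 30% | 56.1% | 64.7% | 8.6 |
| 50% vs 25% | 41.3% | 50.2% | 8.9 |
| 40% vs 10% | 70.5% | 74.3% | 3.8 |

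**Step 5: spread of the gain.** Rates from 5% to 95% were run in both arms, keeping the pairs where Fisher's power is 30% to 90%:

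- 30/30, 0.05: 2.5 to 9.2 points, mean 6.0.
- 29/31, 0.05: 0.3 to 8.9 points, mean 3.3.
- 29/30, 0.05: 0.3 to 9.9 points, mean 3.5.
- 30/30, 0.10: 4.0 to 14.0 points, mean 8.8.

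**Step 6: one table.** For 6/30 vs 14/30, t = 20 and the two tails are equal. So p_F = 2·Σ(k = 0 to 6) C(30,k)·C(30,20−k)/C(60,20) = 0.054, while p_B = 0.030.

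**Step 7: the two-sided definition.** Some software doubles the one-sided Boschloo p-value instead. With equal arms the two definitions agree. At 29/31 they do not: for 4/29 vs 0/31, Fisher gives 0.049 and the doubled version 0.055. At assumed rates of 20% vs 5%, power falls from 41.7% (Fisher) to 32.8% (doubled version).

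**The case against.** The strongest reply is that Fisher's test is standard, controls the error rate and is justified by randomisation. Whether to condition on the event total is a long-standing methodological choice. In a plan that states no alpha, sidedness, allocation ratio, cut-point for bleeding or event rate, exchanging one exact test for another is a small matter. All of that stands, and it limits the point to efficiency.

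A reader might also infer stronger statements that the documents do not support:

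- **That Fisher's true error rate is at most 2.7% with about 30 per arm.** This holds only at exactly 30/30 and nominal 0.05. Moving one patient to the other arm (29/31) raises it to 3.9%, and no document fixes the arm sizes.
- **That the 2.7% describes this plan.** Section 7.1 says alpha will be raised. At nominal 0.10 and 30/30 the true rate is 5.6%.
- **That about 9 points of power are lost.** That is near the top of the 30/30 range and rests on event rates that the documents do not give.
- **That any two-sided Boschloo test is at least as powerful as Fisher's.** Step 7 shows that the doubled version is not when the arms are unequal.
- **That Fisher's test is the plan's only method.** Section 7.1 also names an ANCOVA, and the Study Summary's wording leaves room for further methods. It is the only test named for yes/no outcomes, and it is not assigned to intra-operative re-bleeding.

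What survives does not depend on the assumptions. Whatever the alpha, split or rates, Boschloo's test ordered by the two-sided Fisher p-value cannot reject fewer tables than Fisher's and stays within the nominal level.

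**Conclusion.** The point holds as an efficiency improvement. Nothing in the plan is invalid here. Under an assumed two-sided 0.05, Fisher's test spends 2.7% at exactly 30/30 and 3.6% to 3.9% at the slightly uneven splits examined. The better exact test gains about 2.5 to 9 points of power at 30/30 (mean 6). At 29/31 the mean is about 3, with some rates showing almost nothing. A raised alpha does not remove the difference: at 0.10 and 30/30, with 50% vs 25%, power goes from 53.3% to 63.1%. The direction of the gain is certain, but its size cannot be fixed because alpha, sidedness, split and event rates are all unstated.

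**What to change.** In the Study Summary and section 7.2, name Boschloo's exact test for the yes/no comparison of any transfusion and, if it is to be tested, intra-operative re-bleeding. State that the two-sided version orders tables by the two-sided Fisher p-value and does not double the one-sided p-value.

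State the alpha and sidedness in the same place, and reconcile them with the unspecified increase in section 7.1. Report the risk difference with a 95% interval, and keep Fisher's p-value as a supporting line.

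The cost is protocol wording, with no added patients and no loss of error control. The downside is a less familiar test whose two-sided definition must be prespecified and checked against the software used. The choice must be made before outcome data are seen, because choosing between 0.054 and 0.030 afterwards would not be credible.
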